10.1.1 Subject and Investigator In-clinic Assessment

Subjects will be trained extensively in accurate self-assessment of their glabellar line severity by the investigator at the baseline visit, as outlined in the Instruction Manual for Subject Glabellar Line Severity Self-Assessment. Investigators will complete training before trial initiation and will receive training certification. Subject assessment must be performed independently of the investigator and ideally before the investigator assessment, to rule out any influence or bias from the investigator. The date and time of assessment will be recorded for each visit in the double blind cycle and for the week 4 visits during the open label cycles. Subjects and investigators will assess the severity of the subject's glabellar lines at maximum frown and at rest using the FWS instrument (Section 20.1), i.e. the GLS-S (for subjects) and the GLS-I (for investigators).

In the first treatment cycle, the severity of the subjects' glabellar lines will be evaluated by the subject and the investigator at baseline and at study visits 1, 2, 4, 8, 12 weeks and at 4 weekly intervals thereafter (week 16, week 20, etc.) until the subject qualifies for re-treatment with glabellar line severity returning to a score of 2 or 3 on the FWS. The same investigator must assess the subjects at baseline and at the visits at weeks 1, 2 and 4 in the first treatment cycle, although every effort shall be made to have the same investigator assess subjects at all time points.

The primary efficacy endpoint will be a composite endpoint of the investigators' and the subjects' assessments of line severity at maximum frown in comparison with placebo at week 4. A subject will be considered a responder if they have a FWS score of 0 or 1 and an improvement ≥ 2 points in FWS score (at maximum frown) at the week 4 visit (of the first treatment cycle) relative to baseline, based on both the investigator's and the subject's in-clinic assessments. Responder rates at other time points in the first treatment cycle will be evaluated as secondary endpoints.

In the open label extension phase, the percentage of responders (FWS score of 0 or 1 and an improvement ≥ 2 points in FWS score at maximum frown) at week 4 after re-treatment relative to the rating at the preceding end of cycle visit will be determined as a secondary efficacy endpoint.

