- 1 Depending on the duration of treatment effect, a maximum of 4 treatments is permitted.
- 2 Evaluation for re-treatment takes place at the earliest at 12 weeks after the first/previous treatment. Subjects who do not qualify for re-treatment at week 12 will have the option (pending eligibility) for re-treatment at 4-weekly intervals thereafter, until they are eligible for re-treatment. Once the subject is eligible for re-treatment, the end of cycle procedures will take place and the subject can receive re-treatment (i.e. the end of cycle visit and the re-treatment visit will be conducted on the same day as the Evaluation for Re-treatment visit).
- 3 The latest time for re-treatment is study week 48; if a subject is not eligible for re-treatment at study week 48, the End of Study visit will be completed.
- 4 The End of Study visit can take place in four-weekly intervals from study-week 48 until study-week 60. For subjects receiving re-treatment at week 48, the last cycle will end 12 weeks later at week 60 (=End of Study visit). End of Study visit will take place at week 48 if week 48 visit is an Evaluation for Re-treatment visit and the subject is not meeting the criteria for re-treatment. For subjects having received their last injection 8 weeks or less prior to week 48, the End of Study visit will take place 12 weeks after the last study drug treatment was given, e.g. week 52 if subject was retreated at week 40. For subjects that get prematurely discontinued from the study (at any time) the End of Study visit will take place within 1 week of discontinuation.
- 5 Only in women of child-bearing potential; blood serum test at screening and End of Study visit; otherwise urine dip stick.
- 6 Vital signs include blood pressure (diastolic /systolic) and pulse.
- 7 Laboratory Assessments: Hematology and Serum Chemistry, details in Section 11.15 of the study protocol..

Statistical Analysis Plan (SAP)

- 8 Investigator's assessment of glabellar line severity at maximum frown and at rest. Assessment will be made using the 4-point FWS [GLS-I] (0 =none, 1=mild, 2=moderate, 3=severe) and will be recorded in the CRF.
- 9 Subject's assessment of glabellar line severity at maximum frown and at rest. Assessment will be made using the 4-point FWS [GLS-S] (0 =none, 1=mild, 2=moderate, 3=severe). Subject Assessment will be performed before (ideally) and always independently of investigator assessment and will be recorded in the CRF)

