7.2 Handling of missing data

7.2.1 Missing data analysis methods

Analyses will be performed by visit. For responder analyses on visits at week 4 and week 12, missing in-clinic assessments (investigator or the subject) with the FWS at baseline or week 4 and week 12 visits will be assigned as being non-responders.

As sensitivity analyses, the following additional approaches for handling of missing values will be applied:

- Analysis on observed values only, i.e. missing values will be excluded from analysis.
- Last observation carried forward (LOCF)
- Tipping point analysis: each missing value will be assigned to either a response or non-response, so that all possible combinations of replacing one or more missing

Statistical Analysis Plan (SAP)

values within each treatment group will be analyzed. p-values will be calculated for each combination and graphically displayed using a scatter plot.

The analysis of the week 16 visit regarding the endpoint ‘percentage of responders at week 16 (after first treatment)’ will be conducted on observed values only, i.e. missing investigator or the subject in-clinic assessments with the FWS at baseline or week 16 visit will be excluded from analysis but not assigned as being non-responders. The same approach holds for the endpoint ‘percentage of responders at week 20 or later (after first treatment)’ respectively.

All analyses of the modified Skindex-16 (GL-QoL) Emotional and Functioning domain and overall scores will be conducted on observed values only, i.e. missing domain and overall scores will be excluded from analysis; no imputation of missing domain and overall scores will be performed. The same approach will be followed for the analyses of the FACE-Q scales.

The analysis of “responder” 4 weeks after re-treatment will be conducted on observed values only, i.e. subjects with missing investigator or the subject in-clinic assessments on FWS week 4 or at the preceding end of the cycle visit will be excluded from analysis.

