In general, the same statistical analyses, inclusive the additional exploratory analyses as described for the primary endpoint, will be conducted.

The analysis using the investigator’s in-clinic assessment will be conducted first with respect to the hierarchical order of key secondary endpoints, with the analysis using the subject’s in-clinic assessment second.

Statistical Analysis Plan (SAP)

All analyses (inclusive the additional exploratory analyses) on the investigator's in-clinic assessment will be conducted only for subjects who have an investigator's in-clinic assessment of a FWS score at rest > 1 at baseline. This will similarly be applied for the analyses of the subject's in-clinic assessment.

For the primary analysis (to be considered within the hierarchical testing procedure), subjects with missing investigator in-clinic assessments of FWS score at rest at baseline or week 4 visit will be assigned as being non-responders for this endpoint. This will similarly be applied for the subject's in-clinic assessment within the primary analysis.

As a consequence, the primary analysis will lead to exactly the same results as the LOCF analysis and thus the LOCF analysis will be skipped.

Analysis of key secondary endpoint 4: The percentage of responders at maximum frown (as defined above for the primary efficacy endpoint) at week 20 or later (after the first treatment).

The analysis of visit week 20 will be conducted on observed values only, i.e. missing investigator or the subject in-clinic assessments on FWS at baseline or visit week 20 will be excluded from the analysis but not assigned as being non-responders. Subjects who were re-treated before visit week 20 are considered to be non-responders.

In addition, the same analyses, inclusive the additional exploratory analyses as described for the primary endpoint, will be conducted as exploratory analyses (for subgroups also).

Analyses of other visits after first treatment but before re-treatment up to week 48 are exploratory only based on the FAS using descriptive statistics only. Subjects with re-treatment before the respective visit will be excluded from the analysis. Additional exploratory analyses, as described for the primary endpoint, will not be conducted, with the exception of the calculation of 95% CIs.

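### SAP 8.6.3 skips the LOCF sensitivity analysis for key secondary endpoint 3 because it supposedly equals non-responder imputation, which is not so

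*SAP*

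**What the plan says.** SAP 8.6.3 sets the rule for the confirmatory analysis of key secondary endpoint 3. Subjects with a missing FWS score "at rest at baseline or week 4 visit will be assigned as being non-responders for this endpoint". It presents what follows as a consequence of that rule: "the primary analysis will lead to exactly the same results as the LOCF analysis and thus the LOCF analysis will be skipped".

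Other parts of the plan bear on this:

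- **At-rest scores before week 4.** SAP Table 1, footnote 8, describes the investigator's FWS rating as an "assessment of glabellar line severity at maximum frown and at rest", and footnote 9 says the same for the subject. Protocol 10.1.1 has both raters score the "glabellar lines at maximum frown and at rest using the FWS instrument". It sets the cycle 1 timing as follows: the subject's "glabellar lines will be evaluated by the subject and the investigator at baseline and at study visits 1, 2, 4, 8, 12 weeks".
- **LOCF in the general rules.** SAP 7.2.1, on responder analyses at weeks 4 and 12, states: "As sensitivity analyses, the following additional approaches for handling of missing values will be applied". LOCF is on the list, with the observed-values and tipping-point analyses. Protocol 12.3 has the same list.
- **LOCF for the primary endpoint.** SAP 8.6.2 applies the same non-responder rule at the same week 4 visit and keeps LOCF, for the FAS, MFAS and PP.
- **LOCF for endpoint 3 in the protocol.** Protocol 12.4.2 gives endpoint 3 the same additional exploratory analyses as the primary endpoint. LOCF is one of these (Protocol 12.4.1).
- **Declared changes.** SAP section 9 lists two changes from the protocol: the SAF definition and the antibody analysis.

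**The concern.** Non-responder imputation ignores whatever was seen before week 4. LOCF uses it. The two can agree for every subject only if there is never an earlier post-baseline at-rest score that counts as a response, and the visit schedule provides two occasions for such a score. The stated reason for skipping LOCF therefore does not follow from the missing-data rule.

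At stake is one sensitivity analysis that the protocol plans for each rater's version of the endpoint. It disappears because of an incorrect statement, and a reader who checks SAP section 9 for departures from the protocol will not find it there.

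**Working it through.** The plan attaches no figure to the claimed equality, so there is none to reproduce. The check is logical first, then an illustration of size.

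**Step 1: one subject.** At-rest score 3 at baseline, 1 at week 2, week 4 missing.

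- Primary rule: week 4 missing, so non-responder.
- LOCF: the 1 is carried to week 4; 3 − 1 = 2 points of reduction, so responder.

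This holds under both thresholds in the SAP: a reduction of at least 1 point in the endpoint list (SAP 4.2), and of more than 1 point in the analysis text (SAP 8.6.3). That mismatch is a separate matter.

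**Step 2: all possible scores.** Take a subject with week 4 missing and a last earlier post-baseline at-rest score between 0 and 3. The primary rule always gives non-response. LOCF gives response for these pairs (baseline, last score):

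- SAP 8.6.3 text (baseline above 1, reduction above 1): 2 × 4 = 8 pairs, of which 3 respond: (2,0), (3,0), (3,1).
- SAP 4.2 (baseline at least 1, reduction at least 1): 3 × 4 = 12 pairs, of which 6 respond: (1,0), (2,0), (2,1), (3,0), (3,1), (3,2).

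These count possibilities; they are not probabilities.

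**Step 3: when the two do agree.** They agree if nobody is missing at week 4, if no missing subject's last earlier score met the criterion, or if LOCF may carry only the baseline value. The SAP does not state the last, and it would make the LOCF analysis kept for the primary endpoint redundant too. Restricting the analysis by baseline at-rest score does nothing about a missing week 4 score. The MFAS definition (SAP 6.3) asks for an assessment at week 1, 2 or 4, so the plan allows for subjects with early data only.

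**Step 4: size.** In one arm, let m be the share missing at week 4 and e the share of those subjects whose last earlier score was a response (no earlier score counts as non-response). Then

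LOCF rate − non-responder rate = m × e,

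and the treatment difference changes by m_A × e_A − m_P × e_P.

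All inputs here are assumed: m equal in both arms, e_A = 50%, e_P = 15%.

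| m | Active | Placebo | Change in treatment difference |
|---|---|---|---|
| 5% | 0.05 × 0.50 = 2.5 points | 0.05 × 0.15 = 0.75 points | 2.5 − 0.75 = 1.75 points |
| 10% | 0.10 × 0.50 = 5 points | 0.10 × 0.15 = 1.5 points | 5 − 1.5 = 3.5 points |

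A wider assumed range takes m from 2 to 10%, at-rest response of 40 to 60% on active and 10% on placebo, and e at 50 to 100% of those rates.

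- Low end: 0.02 × 0.5 × (0.40 − 0.10) = 0.3 points.
- High end: 0.10 × 1.0 × (0.60 − 0.10) = 5 points.

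The 10% drop-out in SAP section 5 is a rate for the whole study, so 10% missing at week 4 is an upper-end case.

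**The case against.** The case for leaving the plan alone is that little depends on this analysis, and most of that case stands.

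- **Confirmatory results.** A reader might infer that tests 3.1 and 3.2 are compromised. They are not. SAP 8.6.3 takes their p-values from the Cochran-Mantel-Haenszel test with missing counted as non-response, and SAP 8.6.1.1 makes every other method exploratory.
- **Missing data still examined.** Endpoint 3 keeps the other additional analyses of the primary endpoint, including observed values and tipping point. The tipping-point grid covers every split of the missing subjects into response and non-response within each arm, so the responder counts that LOCF would give lie on it. What the grid does not show is which point that is.
- **Caution.** A reader might infer that skipping LOCF hides a threat to a positive result. In the scenarios above, non-responder imputation gives the smaller treatment difference, so it does not. This is not guaranteed: with e_A = 50% and e_P = 15%, the order reverses if placebo missingness exceeds 0.50 / 0.15 = 3.3 times that on active.
- **PP set.** SAP 6.4 requires an FWS assessment by both raters at week 4. Provided the at-rest score is recorded there, LOCF and the primary rule do coincide in the PP. They need not in the FAS or MFAS.
- **Reporting.** A reader might infer that the study report will claim equivalence as a finding. The SAP only gives a reason for omitting an analysis and says nothing about such a claim.

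None of this makes the stated equality true.

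**Conclusion.** The sentence in SAP 8.6.3 is wrong as written. It removes one planned exploratory analysis, for two raters, on a ground that the plan's own visit schedule contradicts, and section 9 does not record the change. Confirmatory inference is untouched and robustness to missing data is still examined, so this is a correction worth making but not a threat to the trial's conclusions.

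The shift of 1.75 to 3.5 points in the treatment difference is illustrative. It rests on an assumed 5 to 10% missing at week 4, equal in the two arms, and assumed earlier response of 50% and 15% among those subjects. The wider assumptions give 0.3 to 5 points. There is no shift if no missing subject's last earlier score was a response.

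**What to change.** Delete the sentence in SAP 8.6.3. State that, for 3.1 and 3.2, LOCF carries the last post-baseline at-rest score (week 1 or week 2) to week 4, separately for investigator and subject, as an exploratory analysis. If the sponsor would rather omit LOCF, it should give a valid reason, for instance that the tipping-point and observed-values analyses suffice, and list the omission in SAP section 9.

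The scores are already scheduled for collection. The cost is one deleted sentence, a line of specification and one extra exploratory table per rater.

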7.3 Eligibility Criteria for Re-treatment

The following criteria **MUST** be met for re-treatment:

- At time of re-treatment subject does not have relevant changes to their health status from enrollment, which would have prevented subject's entry into the study according to the inclusion and exclusion criteria.
- The subject must have been randomized to receive treatment and must have received at least one treatment (BoNT/A-DP or placebo).
- A minimum of 12 weeks must have elapsed since the previous study treatment.
- The subject's glabellar lines at maximum frown must have relapsed to a FWS score of 2 or 3 as determined by both the investigator and the subject.
- No relevant infection or inflammation in the planned injection area.
- Negative urine pregnancy test, in women of child-bearing potential.
- The subject must have received fewer than four study treatments.
- The subject must agree and consent to re-treatment.
- Re-treatment will be performed at the latest by week 48.

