A subject may move to the next treatment cycle if more than 12 weeks have passed since the previous treatment. Starting at week 12 and at 4-weekly intervals thereafter, subjects will attend the site for the Evaluation for Re-treatment visit. If the subject has a Facial Wrinkle Scale (FWS) score (at maximum frown) of ≥ 2 , as determined by both the subject using the Glabellar Line Scale for Subjects (GLS-S) and the investigator using the Glabellar Line Scale for Investigators (GLS-I), this visit on the same day at the same site visit will then be considered the End of Cycle visit and all other criteria required to determine eligibility for re-injection will be assessed e.g. negative urine pregnancy test (in women of child-bearing potential), lack of infection or inflammation in the planned injection area etc. Furthermore, all additional tests e.g. laboratory tests required for final cycle assessment will be performed. If the subject qualifies for re-treatment, on the same day at the same site visit, the subject will then enter the next treatment cycle and will receive the next study drug treatment as part of the Re-Treatment visit (i.e. day 0 of the next treatment cycle).

If the FWS score (at maximum frown) is assessed as ≥ 2 by both the investigator and the subject, but the additional criteria for reinjection are not met, e.g. relevant infection or inflammation at the injection site, the subject may attend for a visit 4 weeks thereafter. Subjects with a positive pregnancy test, or subjects who do not agree to re-treatment, will be withdrawn from the study and the End of Study visit will be conducted at the earliest opportunity.

If at an Evaluation for Re-treatment visit the subject wants to get re-treated, but the investigator does not agree or vice versa (i.e. the FWS score is not \geq at least 2 by both assessments), the subject will return to the site four weeks thereafter for another Evaluation for Re-treatment visit. There is no limit to the number of Evaluation for Re-treatment

Statistical Analysis Plan (SAP)

visits. In order to consider a visit as the End of Cycle visit, there must always be agreement between investigator and subject on a FWS score (at maximum frown) of ≥ 2 .

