4.2 Key Secondary efficacy endpoints

The key secondary efficacy endpoints of this study are:

1. The percentage of responders at maximum frown at week 12 (after the first treatment with BoNT/A-DP or placebo).
2. The percentage of responders at week 16 (after the first treatment).
3. The proportion of subjects with a ≥ 1 point reduction in FWS score at rest at week 4 in the first treatment cycle, based separately on the investigators' and the subjects' in-clinic assessments (applicable only for subjects who have a FWS score at rest ≥ 1 at baseline).
4. The percentage of responders at week 20 or later (after the first treatment).
5. The extent of change in psychological impact (emotional and social functioning and concerns relating to their glabellar lines) at week 4 after the first treatment, in the BoNT/A-DP group in comparison with placebo, relative to baseline, as assessed by the modified Skindex-16 (Glabellar Line Quality of Life Scale [GL-QoL]) and the FACE-Q (Appraisal of Lines Between Eyebrows and Age Appraisal visual analog scales (VAS)), respectively.

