6.6 DRM

For the DRM appropriate listings displaying all relevant data will be provided to the sponsor and serve as a source for the protocol deviations discussion about the classification into major and minor. No unblinding will be done for creation of these listings.

The following protocol deviations will be assessed on a case-by-case basis and a final decision on a possible exclusion from the PP will be done during the DRM:

- Inclusion/exclusion criteria violated
- Use of disallowed medications
- Serious breach of GCP
- Photography not collected or available for all visits
- Site staff performing the study assessment not trained
- Failure to discontinue subjects where appropriate.
- Subject re-treated despite not meeting all re-treatment eligibility criteria

Patients with minor protocol deviations will not be excluded from the PP.

Statistical Analysis Plan (SAP)

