8.6.3 Analysis of secondary efficacy endpoint(s)

The following order of tests will be defined for the analysis of the key secondary endpoints:

- Primary endpoint (composite endpoint)
- Key secondary endpoint 1 (composite endpoint)
- Key secondary endpoint 2 (composite endpoint)
- Key secondary endpoint 3
 - 3.1: The investigator's in-clinic assessments
 - 3.2: The subject's in-clinic assessments
- Key secondary endpoint 4 (composite endpoint)

Statistical Analysis Plan (SAP)

- Key secondary endpoint 5
 - 5.1: The modified Skindex-16 (GL-QoL) Emotional domain
 - 5.2: The modified Skindex-16 (GL-QoL) Functioning domain
 - 5.3: The modified Skindex-16 (GL-QoL) Overall score
 - 5.4: The FACE-Q Appraisal of Lines Between Eyebrows scale
 - 5.5: The FACE-Q Age Appraisal VAS score

For key secondary endpoints 2 – 4, the p-value to be considered within the hierarchical testing procedure is the one resulting from the Cochran-Mantel-Haenszel test as described for the primary efficacy endpoint in the first paragraph entitled “Primary Analysis” of section 8.6.2.

Analysis of key secondary endpoint 1: The percentage of responders at maximum frown (as defined above for the primary efficacy endpoint) at week 12 (after the first treatment with BoNT/A-DP or placebo).

The same analyses, inclusive the additional exploratory analyses, as described for the primary endpoint will be conducted.

Analysis of key secondary endpoint 2: The percentage of responders at maximum frown (as defined above for the primary efficacy endpoint) at week 16 (after the first treatment).

The analysis of the week 16 visit will be conducted on observed values only, i.e. missing investigator or the subject in-clinic assessments with the FWS at baseline or week 16 visit will be excluded from analysis but not assigned as being non-responders. Subjects who were re-treated before visit week 16 are considered to be non-responders.

In addition, the same analyses, inclusive the additional exploratory analyses, as described for the primary endpoint will be conducted as exploratory analyses. Subjects who were re-treated before visit week 16 are considered to be non-responders in all these analyses.

Analysis of key secondary endpoint 3: The proportion of subjects with a > 1 point reduction in FWS score at rest at week 4 in the first treatment cycle, based separately on the investigator and the subject in-clinic assessments

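### After week 20, SAP 8.6.3 drops already re-treated subjects instead of counting them as non-responders, so exploratory late response rates are higher by a factor of 1/(1−s) than under the week-20 rule at the same visit and arm

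*SAP*

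**What the plan says.** Key secondary endpoint 4 (SAP 4.2) covers response at week 20 or later after the first treatment. SAP 8.6.3 gives two rules for subjects who have already been re-treated:

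- Week 20, the tested analysis: "Subjects who were re-treated before visit week 20 are considered to be non-responders".
- Other first-cycle visits up to week 48 (FAS, exploratory, descriptive, with 95% CIs): "Subjects with re-treatment before the respective visit will be excluded from the analysis".

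Week 16 (key secondary endpoint 2) follows the week-20 rule: "Subjects who were re-treated before visit week 16 are considered to be non-responders".

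The lead-in to the exploratory visits, in both Protocol 12.4.2 and SAP 8.6.3, limits them to visits that precede re-treatment. The protocol sets no denominator for them, and SAP 9 does not list the exclusion as a change. SAP 7.2.1 prescribes observed-values-only handling of missing assessments for endpoint 4 but does not say how re-treated subjects count.

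On when re-treatment can happen, Protocol 7.3 says that the lines at maximum frown "must have relapsed to a FWS score of 2 or 3 as determined by both the investigator and the subject". SAP 3.3 requires the same agreement before a cycle can end.

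**The concern.** Response needs a score of 0 or 1 from both raters; re-treatment needs 2 or 3 from both. A subject who has been properly re-treated was therefore seen to be a non-responder on leaving the first cycle. This is an observed failure, not a missing value. Removing such subjects selects the denominator on the outcome, although the analysis is described as based on the FAS.

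The exclusion has effect only after week 20. Nobody can be re-treated before week 12, and weeks 16 and 20 have their own rule. A series of rates from week 16 to week 48 would therefore change its denominator after week 20.

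The late rates bear on the duration-of-effect objective (SAP 2.2, objective 2). They are the only planned description of first-cycle composite in-clinic response after week 20: the photograph endpoint stops at week 20, and SAP 8.6.4 plans Kaplan-Meier analysis only for onset. Rates are shown by treatment group (SAP 8.1), and each arm's rate is raised by that arm's own factor.

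**Working it through.** The documents state no late-visit rate and no share re-treated, so there is no figure of the plan to reproduce on this point. The active-arm size of 525 is from SAP 5. All other counts below are assumed.

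**1. The factor.** For one arm and one visit, let N be the arm size, M the subjects not re-treated whose assessment is missing, R those re-treated before the visit, and X the responders.

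- Week-20 rule: X/(N−M)
- Exclusion rule: X/(N−M−R)
- Ratio: (N−M)/(N−M−R) = 1/(1−s), with s = R/(N−M)

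The ratio does not depend on X, provided that X is above zero. The denominator of s must be classified subjects (observed plus re-treated). For example, with N = 525, 70% of the FAS re-treated (367.5) and 25 missing, s = 367.5/500 = 0.735 and the factor is 3.77. Taking s as 0.70 would give 3.33.

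**2. A range for s in the active arm at week 24.** Protocol 4.5.1.2 cites durations of effect from other studies. Assume that loss of effect leads to re-treatment at or before the week 20 visit.

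- Four to six months, taken as uniform over 17.4 to 26.1 weeks: (20 − 17.4)/8.7 = 0.30
- Median 85 days (12.1 weeks): at least 0.50
- 17.1 ± 6.5 weeks, taken as normal: Φ((20 − 17.1)/6.5) = 0.67

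The factors are 1/0.70 = 1.43, 1/0.50 = 2.0 (at least) and 1/0.33 = 3.0. Protocol 6.1 anticipates a duration of about 12 weeks.

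**3. Illustration.** Assume 525 active subjects, none missing, 105 responders at week 20 and 63 at week 24. Week 20 is 105/525 = 20.0% (Wilson 95% CI 16.8–23.6). Week 24 is then:

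| Rule at week 24 | s | Rate | Wilson 95% CI |
|---|---|---|---|
| Week-20 rule | any | 63/525 = 12.0% | 9.5–15.1 |
| Exclusion | 30% | 63/368 = 17.1% | 13.6–21.3 |
| Exclusion | 40% | 63/315 = 20.0% | 16.0–24.8 |
| Exclusion | 50% | 63/262 = 24.0% | 19.3–29.6 |
| Exclusion | 67% | 63/173 = 36.4% | 29.6–43.8 |

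Responders fall by (105 − 63)/105 = 40%. The exclusion rate therefore exceeds the week-20 rate only if s is above 40%.

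With 52 missing (about 10%), the week-20 rule gives 63/473 = 13.3%. Exclusion gives 63/331 = 19.0%, 63/237 = 26.6% and 63/156 = 40.4% at s of 30%, 50% and 67%. The factors are the same.

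**4. Between arms.** The contrast can move either way. These inputs are assumed.

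- s of 0.7 (active) and 0.9 (placebo), exclusion rates 30% and 10%: a difference of 20 points. The week-20 rule gives 30% × 0.3 = 9% and 10% × 0.1 = 1%, a difference of 8 points.
- s of 0.7 and 0.95, exclusion rates 30% in both arms: no difference. The week-20 rule gives 9% and 30% × 0.05 = 1.5%, a difference of 7.5 points.

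**The case against.** The strongest reply is that there is no contradiction. The two rules govern different visits with different roles, and both are stated openly in the same subsection. The lead-in already confines the exploratory visits to the time before re-treatment, so exclusion is a natural way to carry it out. Response among subjects still in the first cycle is a legitimate descriptive quantity. Counts accompany percentages (SAP 8.1), so a reader can see the denominator shrink. The duration objective is also served by the tested comparisons at weeks 12, 16 and 20.

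Much of this stands. The SAP does state the conditioning, and the choice between the two quantities is one of estimand. The size of the effect also rests on assumptions: s is unknown, the cited studies may define duration differently, re-treatment can lag loss of effect because other criteria and consent are needed, and the responder counts are invented.

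It does not remove the point. A conditional rate among subjects selected for not having relapsed under both raters answers a different question from the rates at weeks 16 and 20, yet it sits under the same endpoint. The plan gives no reason for the switch and no companion rate on the earlier footing. Eligibility breaches, which SAP 6.6 foresees ("Subject re-treated despite not meeting all re-treatment eligibility criteria"), are the only re-treated subjects who might not have been non-responders.

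**Conclusion.** The point holds as one of interpretation. At any first-cycle visit after week 20 and in either arm, the planned rate is higher than the week-20 rule would give by a factor of 1/(1−s), if anyone has been re-treated and there is at least one responder. Under the assumptions above, the active-arm factor at week 24 is about 1.4 to 3.0. The late rates are not comparable with those at weeks 16 and 20.

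A reader might infer three stronger things that the documents do not support:

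- *That the confirmatory result is compromised.* The week-20 test keeps re-treated subjects as non-responders. The later visits are exploratory and descriptive. No test, alpha or hierarchy step changes.
- *That late rates are 1/(1−s) times the actual week-20 rate.* The identity compares two rules at one visit. Take 60/525 = 11.4% at week 20 and, at week 28 with s = 0.8, 15/105 = 14.3%. The ratio across visits is 1.25. The factor of 5 applies to the same-visit rate of 15/525 = 2.9%.
- *That the reported rate must rise after week 20.* It rises only if responders fall by a smaller fraction than s (with no missing assessments). In the illustration it does not rise at s = 30%.

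**What to change.** In SAP 8.6.3, under key secondary endpoint 4, replace the exclusion sentence with the rule already used at weeks 16 and 20: at each visit after week 20, a subject re-treated before that visit counts as a non-responder. Keep observed-values-only handling for other missing assessments, in line with SAP 7.2.1. Reword the lead-in so that it no longer limits these analyses to visits before re-treatment; otherwise it would conflict with the new rule.

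If the conditional rate is kept as well, label it *among subjects not yet re-treated* and show n per arm at each visit.

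The cost is a small text change and one more use of a derivation already specified for weeks 16 and 20. No new data are needed, and every confirmatory analysis stays as written. The reported late rates will be lower.
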